## Lumbar Imaging Reporting with Epidemiology (LIRE) STATISTICAL ANALYSIS PLAN

where  $p_{ijk}$  denotes the probability that  $Y_{ijk}=1$ . Our secondary outcome analysis parallels the primary and will be based on a natural multilevel mixed model, with additional robust secondary analysis provided by GEE. For Aim 1c we will use  $Y_{ijk}=1$  if CT or MR imaging occurs within a specified timeframe (e.g. 90 days or 12 months) after the index imaging event.

**Medical costs (Aim 1d):** Spine-related costs of care will be estimated using two approaches. First, we will use the spine-related RVU calculated in Aim 1a and estimate clinic-level, spine-intervention expenditures using the annual Medicare-determined payment amount per RVU (e.g., CY2013 = \$34.023 per RVU). (reference: <http://www.cms.gov/Outreach-and-Education/Medicare-Learning-Network-LN/MLNProducts/downloads/medcrephyschedfctsht.pdf> )

Second, as a proxy for costs of spine care, we will use a standard set of reimbursement amounts, i.e., CMS-based payments, and estimate clinic-level spine-related aggregate expenditures by applying CPT-based payment amounts to specific spine-intervention events (e.g., imaging, office visits, procedures, other). We will present monthly and annual means, medians, and ranges of clinic-level cost estimates, prior to and subsequent to implementing the epidemiological intervention. We will assess the level of right-skewness in the expenditure estimates and use t-tests to compare arithmetic means for clinic-level expenditures. In the case of considerable skewness, we will test for differences in logarithmically transformed mean clinic-level expenditures (before and after implementing intervention). We will also describe categories of prescriptions ordered, when available in the electronic medical records for a health system, and estimate costs for prescribed spine-related medications

**Analysis for Aim 2:** The hypothesis of Aim 2 is that there will be a differential effect of the intervention according to the imaging modality used. In order to test this hypothesis we will analyze patient-level data according to the appropriate LMM or GLMM given above, but including the interactions between  $Modality_{ijk}$  indicators (modeled using two indicator variables coding CT and MR, with plain film as the reference) and  $Status_{kt}$ . A test of the interaction terms (2 degree of freedom Wald test) will be used to test the null hypothesis that the effect of the intervention does not vary according the imaging modality.

**Analysis for Aim 3:** The hypothesis of Aim 3 is that there will be a differential effect of the intervention according to the results that are found in the imaging report. We will use an additional variable,  $ImageFinding_{ijk}$ , that takes the value 1 if a significant image finding is present, and 0 otherwise (see detail regarding variable specification in protocol). We will test the null hypothesis that the interaction between  $ImageFinding_{ijk}$  and  $Status_{kt}$  is zero using a Wald test.

[figure not shown]
**Power Calculations:** Our UH2 efforts with respect to sample size and statistical power focused on two key items. First, an important aim of our UH2 Working Group 2 was to obtain an accurate clinic and provider count for each health system. We will now randomize  $n=110$  clinics (1,824 PCPs), which is slightly lower than the  $n=128$  clinics (1,898 PCPs) assumed in our initial project application. However, the majority of the clinics that were dropped were those with only one PCP and therefore would not have contributed much information to the analysis. Second, in our Working Group 3 we sought to develop and characterize a composite RVU summary to be used as the primary outcome measure in this study. In our UH2 project application we discussed statistical power in the context of an important secondary outcome measure, a reduction in subsequent opioid prescription rates. We now present statistical power for the primary outcome measure using data from the BOLD Registry to inform key design parameter estimates.

To our knowledge, off-the-shelf calculators do not exist that would adequately characterize statistical power for a stepped wedge cluster randomized trial with a varying number of sampling units between clusters. We therefore utilized simulation methods to generate and analyze data that closely mimics the design characteristics we anticipate for this study. With a simulation approach, we were able to include estimates of both patient and clinic-level variability and implement the proposed primary analysis methods: random intercept linear mixed effects models for RVU outcomes; and generalized linear mixed models for opioid prescription rates. All simulations

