## Lumbar Imaging Reporting with Epidemiology (LIRE) STATISTICAL ANALYSIS PLAN

developed by a colleague at Dartmouth College. Aggregating across CPT codes identified by this algorithm yields the back-specific RVU.

We are currently preparing a manuscript describing this development work as well as a manuscript that directly influences and informs our LIRE UH3 proposal. Using BOLD cohort data, we identified a subset of patients who have had an early lumbar image (MRI/CT or plain film) following an office visit for back pain. Our BOLD cohort manuscript (in preparation) compares the one-year cumulative RVU of early-imaged patients to carefully matched BOLD cohort controls who did not have an early lumbar image. Preliminary results indicate a substantial downstream increase in healthcare utilization for patients who received an early image compared to propensity score matched controls. Patients who underwent a lumbar MRI or CT had a mean one-year RVU of 150 +/- 410, versus 120 +/- 450 for those who had an early plain film, versus 43 +/- 120 for carefully matched controls. Mapping the relative increases of utilization of nearly 80 and 110 RVUs for the plain film and advanced imaging modalities to the example codes shown in Table 2, we see that imaged patients undergo substantially more procedures. Our expectation for the UH3 project is that the insertion of normative prevalence data into lumbar imaging reports will reduce subsequent inappropriate healthcare utilization.

**Secondary Outcomes:** In addition to back-specific RVU, important secondary outcomes will be obtained and derived using electronic medical record data pulls and include: an indicator of opioid prescriptions written within 30 and 90 days after the index image (Aim 1b); subsequent cross-sectional re-imaging within 90 days and 12 months (Aim 1c); and medical costs (Aim 1d). In the BOLD project, we developed mapping algorithms based upon the United States Food and Drug Administration National Drug Codes (NDC) that generate an indicator of whether or not an individual pharmacy record is an opioid analgesic. Similarly, we have enumerated and categorized a listing of CPT codes that indicate cross-sectional lumbar imaging (CT, or MRI).

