**General Analytic Strategy:** To evaluate the effectiveness of inserting epidemiologic evidence into an imaging report we will use longitudinal regression methods such as linear mixed effects models (LMMs) or generalized linear mixed models (GLMMs) for all primary and secondary outcome measures. Mixed models provide an efficient method for analysis of longitudinal or multilevel data and will be the basis of our primary analysis approach. However, correct model specification is required to ensure valid results when using LMMs or GLMMs and we will therefore use robust standard errors for our primary analysis. Therefore, we are effectively adopting a “working” correlation structure through the specification of flexible multilevel models (LMM or GLMM) but will rely on non-parametrically valid robust standard errors for inference where we cluster on the clinic. Secondary analysis will directly use generalized estimating equations (GEE) adopting simple exchangeable correlation models at the clinic level to determine whether conclusions appear sensitive to model specification.

In each analysis we will also consider a ‘washout period’ in the three months prior to the intervention being activated at a clinic, as determined by the randomization schedule. The rationale for a washout period is to reduce or eliminate within-provider cross-contamination of patient outcomes and utilization in the transition period between control and intervention. Including a washout period reduces the risk of having a patient initially treated in the control time period return to their primary care provider for subsequent care after the primary care provider has been exposed to the intervention through other patients. This reduces the potential bias due to within-provider cross-contamination of outcomes on the estimated intervention effect.

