Our primary regression model acknowledges the fundamental multilevel structure of individual-level data collected in health care systems with patients nested within providers, and providers nested within clinics. Although, the basic intervention contrast is the pre-post change associated with the initiation of intervention for each clinic, we do not propose using clinic-level summary measures for inference since the weighting of both patients and providers is not simple when heterogeneity of cluster sizes exists (e.g. PCPs per clinic, and patients per PCP). A proper multilevel model allows for optimal weighting based on the estimated variance components

Lumbar Imaging Reporting with Epidemiology (LIRE)  
STATISTICAL ANALYSIS PLAN

(e.g. Gauss-Markov) and yields both an efficient summary of the overall intervention effect, as well an estimate of the variability in the magnitude of effect across clinics. However, we will not rely on the covariance model being correct for statistical inference and will use a robust (empirical) standard error. With greater than 100 total clusters (clinics) we expect valid inference and proper test size and do not anticipate needing to perform any correction such as the jackknife (recommended when the number of clusters is small).

In our analysis we effectively assume that individual patients are nested within a single provider. However, in practice a patient may change providers during the follow-up year over which the primary outcome is captured. However, our basic mixed model covariance structure will simply use the assigned primary provider at the index imaging time. Therefore, we do not rely on model-based standard errors since the covariance structure may not match the true within-clinic covariance structure. We will use robust standard errors clustering at the clinic level, and therefore our analysis is valid even if there are changes in patient provider leading to an incorrectly specified covariance structure. Robust standard errors remain valid when a covariance model is not correctly specified. Furthermore, key secondary analysis of the primary outcome will directly use GEE and only cluster at the clinic level and provider level linkages are not used (nor needed) for simple GEE analysis.

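### The cost tests named for Aim 1d are t-tests on clinic means with no calendar-time term; this conflicts with the SAP's regression rule for secondary outcomes and, read as before/after, mixes any cost trend into the effect

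*SAP*

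**What the plan says.** SAP, Medical costs (Aim 1d), prices spine care in two ways: Aim 1a RVUs multiplied by a payment rate, and a standard set of CMS amounts applied to individual services. It promises monthly and annual summaries of "clinic-level cost estimates, prior to and subsequent to implementing the epidemiological intervention". The test follows: "We will assess the level of right-skewness in the expenditure estimates and use t-tests to compare arithmetic means for clinic-level expenditures". With considerable skewness, "we will test for differences in logarithmically transformed mean clinic-level expenditures (before and after implementing intervention". No regression model, covariate or time term appears in the paragraph, and it does not say whether the t-test is paired.

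Three other places in the SAP bear on this:

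- Secondary Outcomes lists medical costs among the secondary outcomes.
- General Analytic Strategy prescribes longitudinal regression such as "linear mixed effects models (LMMs) or generalized linear mixed models (GLMMs) for all primary and secondary outcome measures".
- Secondary Outcome Analysis, in text just before the cost paragraph, says that secondary outcomes follow the primary analysis through a multilevel mixed model, with GEE in support.

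For the primary outcome, the SAP also states that "we do not propose using clinic-level summary measures for inference", and it adjusts for calendar time because trends could bias the effect. Protocol section 1 presents control of temporal trends as a feature of the design. The SAP Revisions table does not mention costs, and Protocol section 5.7 names no test for Aim 1d.

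**The concern.** In a stepped wedge trial every clinic moves from control to intervention and none moves back, so each clinic's control data precede its intervention data. The SAP acknowledges this under Secondary Analyses of Primary Outcome, where it notes that time and intervention status are correlated. A before/after comparison of clinic means therefore estimates the intervention effect plus whatever costs did over calendar time. The randomised start dates could separate the two, but only a model with a time term, or a comparison within periods, uses them.

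If the cost paragraph is followed as a before/after test, a falling trend could pass for savings and a rising trend could conceal them. Under the first costing approach, cost is the Aim 1a RVU times a rate. The same RVUs would then be tested with time adjustment in Aim 1a and without it in Aim 1d, and the two answers could disagree.

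A related gap is that the first approach works by "using the annual Medicare-determined payment amount per RVU" without saying whether one year's rate applies throughout. Year-specific rates would add price changes to the calendar trend.

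**Working it through.** The documents give no sample size, power or cost trend for Aim 1d, so there is no planned figure to reproduce. The time gap follows from the rollout schedule.

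**Inputs**

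- Five start dates, April 2014 to April 2016, six months apart (Protocol Appendix C, study design overview).
- A baseline period of two quarters before the first wave (Protocol 5.4), hence October 2013 to March 2014.
- Six accrual periods, t = 0 to 5 (SAP, Primary Analysis), hence 36 months from October 2013.
- A three-month washout before activation (SAP, General Analytic Strategy).
- Assumed: even accrual and, for the pooled figures, equal waves.

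**Step 1: gap within each clinic.** Wave w (1 to 5) has pre-data from month 0 to 6w, with midpoint 3w. Its post-data run from month 6w to 36, with midpoint 18 + 3w. The gap is (18 + 3w) − 3w = 18 months for every wave. With the washout, pre-data end at 6w − 3, the midpoint is 3w − 1.5, and the gap is 19.5 months. Because the gap is the same in all waves, randomising the wave does not cancel it.

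**Step 2: gap if clinic-time is pooled by status.**

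- Control mean date: Σ(6w × 3w) / Σ6w = 990/90 = 11.0 months.
- Intervention mean date: (30×21 + 24×24 + 18×27 + 12×30 + 6×33)/90 = 2250/90 = 25.0 months. The gap is 14.0.
- With the washout, the control mean is 742.5/75 = 9.9 months and the gap is 15.1.

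**Step 3: spurious change** = (1 + g)^(gap/12) − 1, where g is an assumed annual cost trend.

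| Contrast | Gap (months) | 1%/year | 2%/year | 3%/year |
|---|---|---|---|---|
| Within clinic | 18 | 1.5% | 3.0% | 4.5% |
| Within clinic, washout | 19.5 | 1.6% | 3.3% | 4.9% |
| Pooled by status | 14.0 | 1.2% | 2.3% | 3.5% |
| Pooled, washout | 15.1 | 1.3% | 2.5% | 3.8% |
| Within one period | 0 | 0 | 0 | 0 |

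**Step 4: trend that hides a true 5% reduction.** (1/0.95)^(12/18) − 1 = 3.5% per year, or (1/0.95)^(12/19.5) − 1 = 3.2% with the washout. For scale, 5% is the reduction in median RVU for which the SAP reports over 90% power on the primary outcome.

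**Step 5: does time adjustment repair it?** Take a true 5% reduction, a rise of 3% per year and the washout. The before/after contrast expects 0.95 × 1.03^1.625 − 1 = −0.3%. In an illustrative simulation of the same case, a clinic-level regression with linear time estimated −5.1%. In a noise-free check with non-linear trends of the same 36-month total, before/after bias averaged 4.7 to 7.1%. The stepped wedge model with linear time left at most 0.3%.

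**Step 6: the log fallback.** In an illustrative gamma simulation with unequal clinics and short pre-periods in early waves, the log-of-clinic-means contrast was shifted by about +2 to +3% with no trend and no effect. The cause is small-sample bias in the log of a skewed mean. It is separate from calendar time.

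**The case against.** The strongest reply is that the SAP already has a time-adjusted plan for costs. General Analytic Strategy covers every secondary outcome, and the text just before the cost paragraph extends the mixed model to secondary outcomes. The t-tests could then be supplementary clinic-level summaries, and the monthly figures would let a reader see a trend. That reading is possible. However, the cost paragraph never calls its tests supplementary, and they are the only tests it names. The instructions are unreconciled, and an analyst could follow either.

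The contrast is also not fully stated. The arithmetic-mean sentence does not say before/after, and Hypothesis 1d (Protocol sections 3 and 5.7) is worded as a comparison between clinics. A t-test within one period would carry no trend. This stands as a limit on the bias figures. But the cost text does not specify a within-period test, and periods 0 and 5 (two of six) have no concurrent comparator.

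The words introducing the mixed models leave the model family open. They do not stretch to a t-test on clinic means, which is not longitudinal regression.

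A reader might go further and attach a false-positive rate to the plan. The documents do not support that, because they give no cost trend or cost variance. At an assumed 3% per year, the paired test rejected in 19 to 28% of runs with skewed costs, arithmetic means and clinic sizes like SAP Table 1. It rejected in 100% with log-scale costs and equal clinics. Those rates reflect the assumptions, not the design. A dollar figure would be no firmer, since it would rest on one illustrative payment rate.

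Little follows from the Revisions table's silence on costs: it covers models used for the manuscript, and nothing shows that costs were among them.

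**Conclusion.** The point holds in two parts. The conflict between the cost paragraph and the SAP's rule for secondary outcomes is plain on the text. The bias is conditional on reading the tests as before/after, which the log fallback states outright and the surrounding sentences suggest for the t-test. On that reading the gap of 18 months (19.5 with washout; 14.0 or 15.1 if pooled by status) follows from the schedule under even accrual, with equal waves for the pooled figures. The resulting 1.5 to 4.5% spurious change (1.6 to 4.9% with washout) rests on assumed trends of 1 to 3% per year, and its direction is unknown.

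A reader might infer that the trial's main finding is compromised or that costs cannot be evaluated. Neither follows. Aim 1d is worded as exploratory, the primary RVU analysis is time-adjusted, and the model needed for costs is already specified. The paragraph should be corrected before any cost result is interpreted.

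**What to change.** Replace the t-test rule with the Aim 1a stepped wedge model applied to patient-level 12-month spine cost:

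- time-varying intervention status;
- calendar time with the site-by-time terms in the SAP Revisions table;
- the same covariates, with clinic and provider random effects;
- robust standard errors clustered on clinic, with GEE as sensitivity analysis;
- the arithmetic mean as target, through an identity or log link. At one fixed rate, a log-cost model would largely repeat the log(RVU + 1) analysis of the primary outcome.

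For the first costing approach, state that all years are priced at one fixed-year CMS rate. Index images from October 2013 to September 2016 with 12-month follow-up span calendar years 2013 to 2017. The second approach already uses a standard set of amounts. Keep the before/after means, medians and ranges, labelled as descriptive.

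The cost is SAP wording and one further run of a specified model on data already being collected. Precision may fall. In an illustrative simulation the model's standard error was 0.88 to 0.93 times that of the paired arithmetic t-test with Table 1-like clinic sizes, but 1.31 to 1.40 times with equal sizes. The interval could therefore be up to about 40% wider.

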## Lumbar Imaging Reporting with Epidemiology (LIRE) STATISTICAL ANALYSIS PLAN

were conducted using R (version 3.0.1) with the *lmer* and *glmmPQL* functions implementing mixed model estimation.

**Power for Primary Outcome:** In the BOLD Registry we identified 639 patients in the Kaiser Permanente and Henry Ford health systems that had a qualifying lumbar image within 6 weeks of a PCP visit, the majority (74%) of which occurred within 7 days. As one would expect with a measure of health care utilization intensity, patient-level RVUs are positively skewed. In our simulations and in the future analysis of study data, we therefore utilize an approximately normalizing transformation of  $\log(\text{RVU} + 1)$  but will make interpretations regarding effect size back on the original RVU scale.

With log-transformed BOLD Registry RVU data, we fit a linear mixed effects model adjusting for image type (advanced vs. plain film) and study recruitment site and estimated the variance components for clinic (0.026) and the residual error term (1.230). The observed intra-class correlation coefficient (ICC) across clinics was 0.013 (95% CI: 0.000 to 0.046). In this subset of BOLD data, the number of PCPs with multiple patients was too few to inform the PCP-level variance component and it is therefore conservatively included in the error term variance for power simulations.

The numbers of clinics and primary care providers were considered fixed for each simulation and we assumed that each provider would provide data for all study time periods. For a range of potential RVU effect sizes, we generated 1,000 simulated data sets and performed mixed model estimation with each data set. In Figure 2, we show statistical power for the primary outcome measure of PCP spine-related RVU under the proposed study design. The study has greater than 90% power to detect reductions in the median spine-related RVU of 5.0% or larger. For a patient receiving a lumbar CT, a 5% reduction in spine RVU translates into one fewer additional lumbar CT scan on average compared to a patient unexposed to the LIRE intervention.

**Power for Secondary Outcome:** Using the updated clinic and provider listing, we repeated the UH2 power analyses for a reduction in subsequent opioid prescriptions. We again used an average baseline opioid prescription rate of 22%, suggested from the pilot manuscript to anchor the effect size of percent reduction in the baseline rate. A clinic-specific baseline opioid prescription rate was drawn from a Beta( $\alpha=6$ ,  $\beta=20$ ) distribution; we used this rate to draw a baseline opioid prescription rate random effect for each primary care provider using a clinic-specific log-normal distribution. We generated 1,000 simulated data sets using the effect size of a 7.5% reduction in the opioid reported in our UH2 application and evaluated each using a GLMM assuming random intercepts. With 110 clinics randomized, the study remains well powered (88.9% power) to detect a reduction in the rate of opioid prescriptions of 7.5% or larger (e.g. 22% down to 20.4%).

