Our method of random assignment is also relatively novel. We propose to use a stepped wedge cluster design, where the order in which clinics receive the intervention is determined at random and by the end of the random allocation, all clinics will have received the intervention. (40, 41)

Finally, given the rapid spread and adoption of IT clinical tools, like the EMR and templates for radiology readings, finding ways to capitalize on the technology itself to positively influence the process of care will make the mammoth nationwide clinical IT investment much more compelling. This project is truly

emblematic of the kinds of innovative thinking that needs to be applied to the clinical IT world to derive the maximum benefit of the tools meant to deliver better and more efficient care.

3. Specific Aims

This study is a pragmatic cluster randomized controlled trial, randomly assigning primary care clinics at four sites, to receive either standard lumbar spine imaging reports or reports containing epidemiological benchmarks for common imaging findings. Our primary outcome will be a metric of back-related intervention intensity, measured passively using the electronic medical record (EMR). The primary analysis will focus on clinic-level changes by using aggregate patient-level data.

Aim 1: To determine whether inserting a description of age-specific prevalence of imaging findings among asymptomatic subjects into lumbar spine imaging reports decreases back-related interventions (imaging, injections, surgeries, etc.) over the subsequent year.

Aim 1a: To determine if inserting epidemiological evidence reduces Relative Value Units (RVUs) attributable to spine interventions (imaging, injections, specialist referrals, surgeries, etc.).

Hypothesis 1a: After primary care clinics are randomly assigned to receive the modified report, they will have a lower average overall RVU (technical and professional) per imaged-patient attributable to spine interventions than when clinics are not receiving the modified reports. Spine interventions reflect visits, tests, and procedures and are patient centered, having both direct and indirect impacts on patients.

Aim 1b: To determine if inserting epidemiological data decreases opioid prescriptions.

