**Primary Analysis:** The primary longitudinal model for back pain specific RVUs will use a time-varying intervention status indicator  $Status_{kt}$  (0 = control, 1 = intervention, for clinic  $k$  at time  $t$ ). Use of the time-dependent intervention status indicator permits both within-clinic contrasts that inform intervention effects (post-versus pre-intervention) as well as contrasts across clinics with different intervention statuses within each time period. The specific regression model will adopt a functional form given below, with fixed effects for time (linear), age (18-39, 40-59, 60+, using two dummy variables), imaging modality type (plain film, CT, MRI using two dummy variables), and clinic size (small, medium, large, using two dummy variables), and site (Group Health Cooperative, Henry Ford, Kaiser Permanente, Mayo Clinic, using three dummy variables) in addition to random

Lumbar Imaging Reporting with Epidemiology (LIRE)  
 STATISTICAL ANALYSIS PLAN

effects for provider, clinic, and intervention status:

[figure not shown]
$$Y_{ijk} = \beta_0 + \beta_1 \cdot Time_t + \beta_2^T \cdot Age_{ijk} + \beta_3^T \cdot Modality_{ijk} + \beta_4^T \cdot Size_k + \beta_5^T \cdot Site_k + \lambda_0 \cdot Status_{kt} + \quad \text{mean model}$$

$$b_{k,0} + b_{k,1} \cdot Status_{kt} + \quad \text{clinic random effects}$$

$$a_{jk,0} + e_{ijk} \quad \text{provider random effects and errors}$$

We will collect the outcome measure  $Y_{ijk}$  on patient  $i$  ( $i=1,2,\dots,n_j$ ) under primary care provider  $j$  ( $j=1,2,\dots,n_k$ ) enrolled in time period  $t$  ( $t=0,1,2,\dots,5$ ) in order to evaluate the overall effect of the intervention at the level of the clinic  $k$  ( $k=1,2,\dots,110$ ). Note that we will collect a single outcome measure for each subject recording the total utilization (RVU) over the 12 months after the index imaging event. Given that the random effects structure may contain additional elements (see below) we will use a robust standard error to test the null hypothesis that  $\lambda_0 = 0$ . For example, using SAS PROC MIXED we can use the “empirical” option in order to obtain robust standard errors. Alternatively, use of the jackknife (at the clinic level) provides a robust standard error estimate (if using R and *lmer*) that is simple to compute.

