**Figure 2:** Hypothetical example of study data showing random clinic intercepts and intervention effects. Each line shows the expected profile for a specific clinic. Here clinic 1 initiates intervention at quarter=2 while clinic 2 initiates at quarter=4.

**Key Model Parameters:** The primary parameter of interest is  $\lambda_0$ , which represents the average effect of the intervention adjusting for temporal trends ( $Time_t$ ), clinic characteristics ( $Site_k$ ,  $Size_k$ ), and individual covariates ( $Age_{ijk}$ ,  $Modality_{ijk}$ ). In order to interpret the random effects structure we focus on clinic level means removing covariate effects where we have: adjusted mean at clinic  $k$  for times prior to intervention =  $\beta_0 + b_{k,0}$ ; and the adjusted mean at clinic  $k$  for times after start of the intervention =  $\beta_0 + b_{k,0} + \lambda_0 + b_{k,1}$ . For clinic-specific means we average over both providers ( $a_{jk,0}$ ) and patients ( $e_{ijk}$ ). Using this representation

we interpret  $\beta_0$  as the pre-intervention adjusted overall mean outcome averaging across all clinics, and  $b_{k,0}$  is the difference between that adjusted overall mean and the pre-intervention (baseline) mean for clinic  $k$ . The variance,  $var(b_{k,0})$ , is a measure of the variation in the baseline mean outcome across clinics. The change in the adjusted mean outcome for clinic  $k$  is given by: (post-intervention adjusted mean) – (pre-intervention adjusted mean) =  $(\beta_0 + b_{k,0} + \lambda_0 + b_{k,1}) - (\beta_0 + b_{k,0}) = \lambda_0 + b_{k,1}$ . Here  $\lambda_0$  represents the average intervention effect across all clinics and  $b_{k,1}$  represents the difference between that average intervention effect and the intervention effect for clinic  $k$ . The variance,  $var(b_{k,1})$ , is a measure of the variation in the change associated with intervention across clinics, or a measure of the heterogeneity of the intervention effect.

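### Hypothesis 1a concerns average RVU, but the log(RVU+1) analysis announced in the SAP's power section estimates a geometric-mean (median) ratio; the SAP states no assumption linking the two and plans no adjusted analysis of the mean

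*SAP*

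**What the plan says.** - **Hypothesis (Protocol section 3 and section 5.7, Hypothesis 1a).** Once clinics receive the modified report, "they will have a lower average overall RVU (technical and professional) per imaged-patient attributable to spine interventions". The target is a mean per patient.
- **Model (SAP, Primary Analysis).** The equation is written for Y with no log. The data behind Y are described as a single measure per subject "recording the total utilization (RVU) over the 12 months after the index imaging event". Under Key Model Parameters, λ₀ "represents the average effect of the intervention adjusting for temporal trends".
- **Scale (SAP, Power for Primary Outcome).** Because RVUs are positively skewed: "In our simulations and in the future analysis of study data, we therefore utilize an approximately normalizing transformation of" log(RVU+1), "but will make interpretations regarding effect size back on the original RVU scale". No rule for returning to that scale is given.
- **Power (same section).** The study is said to have "greater than 90% power to detect reductions in the median spine-related RVU of 5.0% or larger". The next sentence says that, for a patient with a lumbar CT, a 5% reduction "translates into one fewer additional lumbar CT scan on average compared to a patient unexposed" to the intervention.
- **Revisions table at the end of the SAP.** It changes the number of clinics, covariates, time coding, the imaging-findings variable and the opioid outcome. It says nothing on the RVU scale.

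**The concern.** Four descriptions of the primary quantity stand side by side: a mean in the hypothesis, an unlogged equation, a log analysis and a median in the power statement. An analyst who followed the Primary Analysis section literally and one who followed the power section would estimate different things.

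If the log scale is used, the coefficient compares geometric means. That is a legitimate target, but it gives little weight to the high-RVU tail, where surgery sits (fusion is 71.60 RVU in SAP Table 2, against 1.07 for a two-view plain film). Average RVU depends heavily on that tail. The trial could report a significant log-scale reduction while average RVU had not changed, or miss a change in the average that came from the tail. Robust standard errors protect the variance estimate; they do not change which quantity is estimated.

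**Working it through.** **Inputs.** From SAP, Power for Primary Outcome: log-scale variances 0.026 (clinic) and 1.230 (residual), total 1.256; effect 5%. From the SAP's account of the preliminary cohort results, under Primary Outcome: mean one-year RVU 150 after early MR or CT. From SAP Table 2: 6.27 RVU for a lumbar CT without contrast. A lognormal shape for RVU+1 is my assumption.

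**1. The SAP's own illustration.** 0.05 × 150 = 7.5 RVU, and 7.5 / 6.27 = 1.20 CTs. One CT on average therefore reproduces from the reported mean and is slightly conservative. A 5% reduction equals exactly one CT at a mean of 6.27 / 0.05 = 125.4 RVU.

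**2. When the median ratio is also the mean ratio.** If log(RVU+1) is normal with mean μ and variance v, then
- median of RVU+1 = exp(μ)
- mean of RVU+1 = exp(μ + v/2)

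If the intervention shifts μ by λ and v by Δv, then
- median ratio = exp(λ)
- mean ratio = exp(λ) × exp(Δv/2)

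With Δv = 0 the two agree. A simulation with 4 million draws per arm, v = 1.256, starting mean 150 and λ = ln(0.95) gave a mean falling from 150.1 to 142.4 (ratio 0.949) and a median falling from 79.7 to 75.5 (ratio 0.948). The small departures from 0.950 come from the added 1.

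**3. How much change in spread matters.** The mean is unchanged when 0.95 × exp(Δv/2) = 1, so Δv = −2 ln(0.95) = 0.103, and 0.103 / 1.256 = 8.2%. In patient terms, the log SD goes from √1.256 = 1.121 to √1.359 = 1.166. At the 10th and 90th percentiles (z = ∓1.28) the log-scale changes are −0.051 − 1.28 × 0.045 = −0.109 and −0.051 + 1.28 × 0.045 = +0.006. That is a reduction of about 10% at the 10th percentile, 5% at the median and essentially none at the 90th. In the other direction, a fall in log variance of 0.103 would give a mean ratio of 0.95 × 0.95 = 0.90, a larger benefit than the log analysis shows.

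**4. Whether another planned analysis covers the mean.**
- The GEE sensitivity analysis (SAP, General Analytic Strategy and Secondary Analyses of Primary Outcome) has no stated outcome scale. If it follows the power section, it too is on logs.
- The cost analysis (SAP, Medical costs) compares arithmetic means of clinic-level expenditure before and after the intervention by t-test. No covariate or calendar-time adjustment is described, and it moves to logs if skewness is considerable.

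If the log scale is used throughout, no covariate-adjusted, clinic-clustered analysis of mean RVU is planned.

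**The case against.** The best defence is that the transformation is pre-specified. The model equation uses a generic Y, the RVU sentence describes what is collected, and the power section says in terms that the study data will be logged. The averaging in λ₀ is over clinics and need not mean arithmetic-mean RVU. Logging skewed utilisation data is an ordinary choice. Under the constant shift that the model implies, mean and median fall by the same percentage, so the hypothesis is answered either way. The divergence in step 3 is hypothetical, and the cost aim does look at arithmetic means.

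Much of this stands. The log scale is not a post hoc choice, and a constant shift would close the gap. But the SAP does not state that assumption, and the protocol gives some reason to doubt it: Hypothesis 3 expects larger reductions in patients without clinically important findings. If those patients also have lower RVUs (an assumption), spread would widen. Variation between clinics alone is unlikely to do it: added variance equal to the baseline clinic component, 0.026, is only a quarter of 0.103. The cost t-test is no substitute, because in a stepped wedge an unadjusted before/after comparison is confounded with calendar time.

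A reader might also infer that the CT illustration is overstated, by applying 5% to a median. The documents do not support this. The sentence speaks of an average, and it reproduces from the reported mean. No median is reported. One derived from the mean of 150 would be about 80 RVU using log variance 1.256, or about 52 if 410 is read as an SD. The sources disagree because that SD implies a coefficient of variation of 410 / 150 = 2.73, against √(exp(1.256) − 1) = 1.58 from the log variance.

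**Conclusion.** The inconsistency in the target quantity is real and worth correcting, as a cheap improvement; it does not invalidate the trial. The planned log analysis validly estimates a ratio of geometric means of RVU+1. It supports Hypothesis 1a as worded only if the intervention leaves the log-scale spread unchanged. A rise in log variance of about 0.10, or 8%, would cancel a 5% median reduction in the mean. That figure rests on a lognormal shape and on the SAP's total log variance of 1.256, estimated from 639 patients in two health systems after adjustment for image type and site. The documents do not show that such a change is likely, only that nothing planned would reveal it.

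The CT sentence holds on the condition that the 5% applies to the mean. That mean pools MR and CT, and the sentence reporting it does not say that it is restricted to spine-related care.

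A reader might further infer that an untransformed analysis would be badly underpowered. The documents do not support a figure for this: the spread given with the mean is not identified as an SD, the number of patients per provider used in the simulations is not stated, and the power section does not plan that analysis.

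**What to change.** 1. In SAP, Primary Analysis, write the outcome as log(RVU+1). Under Key Model Parameters, define exp(λ₀) as the ratio of geometric means of RVU+1, read as a ratio of medians if the logs are symmetric. State that it equals the mean ratio only if the log-scale spread is the same under control and intervention.
2. Pre-specify, as the key secondary analysis of Hypothesis 1a, a GEE with log link on untransformed 12-month RVU, with the covariates of the primary model as amended and robust standard errors clustered on clinic. Report its ratio of means beside the primary result, and say that this is the analysis that addresses average RVU.
3. Keep the CT illustration, but show its arithmetic (0.05 × 150 / 6.27 = 1.2 CTs) and add that it assumes the 5% reduction also applies to the mean of 150 RVU.

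The cost is a few sentences and one extra model on data already collected. The downside is that the interval for the mean ratio will be wide, because mean RVU is driven by a small number of high-RVU patients.
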